The study's initial visit will occur while patients are in the CTU or fast-track area as they get ready for treatment. The entire study will be explained to the patient when they are preparing for their chemotherapy regimen in a comfortable area provided by the SCCC. After answering the potential participants' questions, the study team member will go through the study's informed consent process if the participant is interested and willing to consent. The potential participants will have time to review and discuss informed consent. After the patient signs the informed consent, the participant will be randomized to the control or the intervention arm.

On the same day, the study team member will meet the participant in the CTU while they receive their infusion and provide both the control and intervention groups, access to complete, via iPad or laptop, the electronic pre-assessment and demographic form, psychological distress VAS, resilience scale, FACIT-G, and a study packet that includes the Antiemesis (MAT) tool, antiemetic diary or antiemetic/aromatherapy diary. The study packet will be completed and returned to the study team member on the participants' next scheduled chemotherapy infusion. The study team member will explain to the participants how to use the MAT tool and how to fill the antiemetic diary or antiemetic/aromatherapy diary. The study team member will go through the instructions to ensure that they understand the forms and how to complete them.

Arm 1 - Control group:

Participants in the control group will receive standard medical care, consisting of antiemetic medicine at the first sign of CINV on a schedule as prescribed by the healthcare provider. The study team member will review with the participant how to use the weekly study packet (e.g., MAT tool and antiemetic diary) and explain that a study team member will collect the packet on their next scheduled chemotherapy infusion.

Arm 2 - Intervention group:

Participants in the intervention group will receive an aromatherapy inhaler for complementary use with their antiemetic medication. Participants will be encouraged to use the aromatherapy inhaler at the first sign of CINV before taking their antiemetic medications that are labeled "as needed". The interventional group will be instructed that one normal inhale is equivalent to one dose of aromatherapy and must report essential oils sensitivity to a study team

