member. The participant will be withdrawn from the study if essential oils sensitivity is identified. Aromatherapy will be used as often as needed or whenever CINV is encountered. Participants are advised to take their prescribed antiemetic medications that are labeled "as needed" as directed by their healthcare provider if they find insufficient comfort change in their CINV after using the aromatherapy. The study team member will explain to the participants that they will need to fill out the MAT tool and antiemetic/aromatherapy diary. And study team member will collect the packet on their next scheduled chemotherapy infusion.

Visit 1: Participants' visit one will take place on their next scheduled chemotherapy infusion – i.e., the participants' first chemotherapy cycle during their study period.

Arm 1 - Control group:

A study team member and participant will meet during the participant's scheduled CTU appointment to collect their MAT tool and antiemetic diary. During this interaction, the study team member will reinforce instructions and answer any participant's questions, concerns, or confusion regarding the MAT tool and antiemetic diary. A new study packet will be provided to the participants.

Arm 2 - Interventional group:

A study team member and participant will meet during the participant's scheduled CTU appointment to collect their MAT tool and antiemetic/aromatherapy diary. During this interaction, the study team member will reinforce instructions and answer any participant's questions, concerns, or confusion regarding the aromatherapy inhaler, MAT tool, and antiemetic/aromatherapy diary. A new study packet and an aromatherapy inhaler, if necessary, will be provided to the participants.

Visit 2: Participants' visit two will take place on their next scheduled chemotherapy infusion – i.e., the participants' second chemotherapy cycle during their study period.

Arm 1 - Control group:

A study team member and participant will meet during the participant's scheduled CTU appointment to collect their MAT tool and antiemetic diary. During this interaction, the study team member will reinforce instructions and answer any participant's questions, concerns, or confusion regarding the MAT tool and antiemetic diary. A new study packet will be provided to the participants.

Arm 2 - Interventional group:

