The participants will complete a pre-assessment and demographic checklist that assesses their demographic information (e.g., race, ethnicity, age, and education level), essential oils sensitivity, and risk factors of CINV. The pre-assessment demographic checklist will provide the descriptive characteristics of the study's sample population.

• Additional data, such as medical history (e.g., diagnoses, allergies, medications, cancer history, and treatment regimen), family history, and recent outpatient and inpatient clinic or hospital visits, will be extracted from the electronic health record.

Aromatherapy Inhaler (Arm 2 – Intervention Only):

The study's aromatherapy inhaler can be used when participants' have their first sign of CINV and as needed. The aromatherapy inhaler contains a proprietary blend of peppermint, spearmint, lavender, and ginger essential oils that can last up to 6 months. Participants will twist open the cap, hold the inhaler below their nose, and take deep breaths to activate the aromatherapy inhaler. Once the participant is done, they will close the aromatherapy inhaler to turn it off. The aromatherapy vapors can be safely inhaled for as long as it takes to provide comfort and relief for the patient. There are no "limits" or duration restrictions for any essential oils in the blend. The aromatherapy inhalation amount can vary from brief intermittent use to continuous inhalation over several minutes. The aromatherapy inhaler has unlimited uses with no time limits. One inhalation of aromatherapy is equivalent to one dose. There are no known contraindications. At each study visit, the study team member will offer the participant a replacement aromatherapy inhalation device.

Antiemetic/Aromatherapy Diary (Arm 2 - Intervention Only):

The antiemetic/aromatherapy diary will allow the participants to record their weekly usage (date and time) of aromatherapy and antiemetic uses and evaluate the aromatherapy and type (name) of antiemetic medications. The evaluation will assess the effects of the aromatherapy on CINV by capturing the number of inhalations per nausea episode and asking the participants, 'Did the aromatherapy take away your nausea?' answers include: 'it took away my nausea completely' to 'it had no effect on my nausea.' If the participants cannot get relief from the aromatherapy, the participants will take the prescribed antiemetic, and the participants will document the type of antiemetic medication they needed.

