All endpoints will be evaluated using parametric analysis to examine the difference between the two conditions across the 3-time points for primary endpoints (CINV and Use of Antiemetics) and 2-time points for secondary endpoints (resilience, psychological distress, and quality of life). The analysis will be conducted using SPSS Version 26. For binary outcomes (CINV), logistic regression will be used. For continuous outcomes (antiemetic use, resilience, psychological distress, and quality of life) a Mixed ANOVA will be used with condition as the between-subjects variable and change over time on the outcome as the within-subjects variable. Sphericity and homogeneity of variance assumptions will be tested prior to interpretation of the results, and the

Greenhouse-Geisser correction will be implemented if Sphericity is violated. A type I error rate of .05 will be used to determine significance for all analyses.

Outcome	Measure	Type of measurement
CINV	MAT	Binary
Use of antiemetics	Antiemetic Diary	Continuous
Resilience	CD-RISC	Continuous
Psychological Distress	Visual Analog Scale	Continuous
Quality of Life	FACIT-G	Continuous

2. Analysis of the Primary Endpoint(s)

For CINV, logistic regression will be used to determine whether the use of aromatherapy decreases the risk for any of the following outcomes: acute nausea, delayed nausea, acute vomiting, or delated vomiting. For use of antiemetic medication, a Mixed ANOVA will be used to evaluate differences between conditions (aromatherapy group vs. treatment as usual) across the 3-time points (Visit 1, Visit 2, and Visit 3). Time x treatment effects will be evaluated as well as main effects.

3. Analysis of the Secondary Endpoint(s)

For resilience, psychological distress, and quality of life, a Mixed ANOVA will be used to evaluate differences between conditions (aromatherapy group vs. treatment as usual) across the 2-time points (Initial visit and final visit). Time x treatment effects will be evaluated as well as main effects

4. Baseline Descriptive Statistics

Participant demographic characteristics will be analyzed using descriptive statistics. Specifically, frequencies and percentages will be reported for categorical variables, and means and standard deviations will be reported for continuous variables.

12) **Provisions to Monitor the Data to Ensure the Safety of Subjects***

This section is not applicable. The risks of this study are minimal.

13) Withdrawal of Subjects*

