The Study's intervention group uses an aromatherapy inhaler, leading to a potential sensitivity to essential oils. Participants will be informed that in the case they have a sensitivity to essential oils, they need to stop using the inhaler and contact the Study PI immediately. The participant will be withdrawn from the Study and encouraged to see their healthcare provider.

There are no foreseeable participant risks or inconveniences related to participation in the research. The participants are free to withdraw at any time, and their decision to participate, refuse, or withdraw will have no impact on their treatment or any other relationship with SCCC. There is no economic burden for the participants.

The participant will be considered "lost to follow-up" if they stop communicating with the study team. The participant will also be considered "lost

to follow-up" if the participant's oncologist withdraws them from IV moderate to high emetogenic chemotherapy.

14) **Risks to Subjects***

Quality assurance will follow the University of Miami School of Nursing and Health Sciences quality assurance guidelines. These include minimizing potential harm for the participants.

The study measures include questions regarding well-being, some of which may cause emotional distress or discomfort. Participants will be informed that they may refuse to answer any question if they do not feel comfortable answering it. If a participant expresses or demonstrates emotional distress, the participant will be encouraged to contact the Sylvester Comprehensive Cancer Center (SCCC) Cancer Support Services for an appointment at [contact] or [contact].

The study's intervention group uses an aromatherapy inhaler, leading to a potential sensitivity to essential oils. Participants will be informed that in the case they have a sensitivity to essential oils, they need to immediately stop using the inhaler and contact the PI of the study, [name]. The participant will be withdrawn from the study and encouraged to see their healthcare provider.

There are no foreseeable participant risks or inconveniences related to participation in the research. The participants are free to withdraw at any time, and their decision to participate, refuse, or withdraw will have no impact on their treatment or any other relationship with SCCC. There is no economic burden for the participants.

Unanticipated Problems (Adverse Events and Serious Adverse Events) a) Definition of Unanticipated Problems

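### Essential-oil sensitivity removes Arm 2 participants from the whole study, with no further data collection or as-randomised analysis stated, and the rules for recording these reactions conflict

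*Combined protocol and SAP*

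**What the plan says.** **Withdrawal.** Sections 13 and 14 tell an intervention participant with sensitivity to stop the inhaler and contact the principal investigator. A separate sentence follows: "The participant will be withdrawn from the Study and encouraged to see their healthcare provider". Section 14 repeats this under unanticipated problems. The Arm 2 instructions in section 9 agree: "The participant will be withdrawn from the study if essential oils sensitivity is identified".

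**Timing.** Section 9 places randomisation straight after consent: "After the patient signs the informed consent, the participant will be randomized to the control or the intervention arm". Both arms then complete the pre-assessment checklist, which asks about "essential oils sensitivity, and risk factors of CINV". No rule is given for a control participant who reports sensitivity there.

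**Analysis.** Under General Approach in section 11, antiemetic use (Visits 1 to 3) and resilience, distress and quality of life (initial and final visit) go into a Mixed ANOVA, where the "Greenhouse-Geisser correction will be implemented if Sphericity is violated". For the primary outcome, "For binary outcomes (CINV), logistic regression will be used"; how the three visits enter that model is not described. No analysis population or method for missing data is named.

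**Recording.** Section 14 classes inhaler sensitivity as an adverse event with no grade limit and assigns adverse events to the HSR-4A non-serious log. It later has the principal investigator investigate all AEs and SAEs, then restricts capture to inhaler-related events of Grade 3 or higher.

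**The concern.** Stopping a treatment and leaving a trial are different events. Here the first triggers the second, and only participants given the inhaler can trigger it by reacting to it. If the people removed differ in outcome from the rest of their arm, the comparison is no longer between the groups that were randomised. The bias is zero if withdrawal is unrelated to outcome. It favours the inhaler if those removed would have done worse, and disfavours it if they would have done better.

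The planned analysis may widen the loss. A standard Mixed ANOVA drops anyone missing a time point, so a participant withdrawn after Visit 1 would also lose the diary already returned. For CINV, the plan leaves it unclear whether MAT forms returned earlier would be kept.

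The recording conflict affects harms. A Grade 1 or 2 reaction that ends participation must be logged under one rule and is not captured under the other, so the reported harms could omit milder reactions.

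**Working it through.** The plan has no figure to reproduce here. Section 6 gives 100 participants without power, effect size, event rate or dropout allowance, and no sensitivity rate appears anywhere. What follows is scale only.

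**Inputs**
- n = 50 per arm: 100 in total (section 6), 1:1 allocation assumed because no ratio is stated.
- r, the as-randomised CINV risk in both arms (no true effect): 0.40 and 0.71, from section 4. The 71% is nausea in breast cancer patients. Neither figure is a planning assumption. Trial risk may exceed 40%, because section 5 requires nausea or vomiting after the first infusion.
- m, the number withdrawn from Arm 2: 1 or 5, both assumed.
- q, the CINV risk among those withdrawn: 1 (all affected) or 0 (none affected).
- Alpha 0.05 (section 11), taken as two-sided because the plan does not say.

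**CINV, withdrawn participants removed completely**

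Observed Arm 2 risk = (50r - mq)/(50 - m). SE of the risk difference at 50 per arm = sqrt(2r(1 - r)/50), which is 0.098 at r = 0.40 and 0.0908 at r = 0.71.

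| r | m | q = 1 | q = 0 |
|---|---|---|---|
| 0.40 | 1 | (20 - 1)/49 = 0.388, -1.2 points | 20/49 = 0.408, +0.8 points |
| 0.40 | 5 | (20 - 5)/45 = 0.333, -6.7 points (0.68 SE) | 20/45 = 0.444, +4.4 points (0.45 SE) |
| 0.71 | 1 | (35.5 - 1)/49 = 0.704, -0.6 points | 35.5/49 = 0.724, +1.4 points (0.16 SE) |
| 0.71 | 5 | (35.5 - 5)/45 = 0.678, -3.2 points (0.36 SE) | 35.5/45 = 0.789, +7.9 points (0.87 SE) |

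If q = r the shift is zero.

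**False rejection under no effect**

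P(|Z + shift/SE| > 1.96) is at most 0.053 for m = 1. For m = 5 it is 0.104 (r = 0.40, q = 1) and 0.140 (r = 0.71, q = 0).

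**CINV, visits pooled and the Visit 1 form kept**

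Two of three forms are lost per person withdrawn: (150r - 2mq)/(150 - 2m). For m = 5:
- r = 0.40, q = 1: (60 - 10)/140 = 0.357, -4.3 points.
- r = 0.71, q = 0: 106.5/140 = 0.761, +5.1 points.

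**Mixed ANOVA outcomes**

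If those withdrawn differ from their arm by an assumed 1 SD, the Arm 2 mean shifts by m/(50 - m) SD: 1/49 = 0.020 for m = 1 and 5/45 = 0.111 for m = 5. Divided by sqrt(2/50) = 0.2, these are 0.10 and 0.56 SE.

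**Power**

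For a standardised difference of 0.50, power is 70.5% with 50 per arm and 68.2% after losing 5 from Arm 2. Precision is not the main issue; selective loss is.

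**Recording rules side by side**

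A related, non-serious Grade 3 reaction can satisfy both rules. A Grade 1 or 2 reaction cannot: it goes on the log under the first rule and falls outside capture under the second. The duty to investigate all events does not say what is recorded.

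**The case against.** The strongest objection is rarity. Sensitivity is an exclusion criterion (section 5) and is checked before consent (section 23), so few participants should be withdrawn. At 1 of 50 even the extreme case barely moves the error rate. The larger figures need 5 of 50 with all or none of them having CINV. If those withdrawn differed by a milder, also assumed, 20 points, 5 of 50 would shift the risk by only 5 × 0.20/45 = 2.2 points. The +7.9 case is especially strained, because entry requires earlier nausea or vomiting, and the 71% comes from breast cancer while section 5 excludes hormone-sensitive cancers. All of this stands and limits the weight of the point.

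Second, the missing analysis population and missing-data method affect every exit in section 13, in both arms. That is true. But sensitivity is the exit where the protocol orders removal from the study for a reaction to the assigned intervention, so it deserves its own correction.

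Third, a control participant has no inhaler to stop, so the control-arm gap is marginal. This is fair; what remains is how a sensitivity answer found after randomisation is handled.

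Fourth, the silence is only partly observable. The consent form, the standard operating procedures mentioned in section 11 and some text around sections 21 and 30 were not available, and nothing says earlier data are discarded. Complete-case loss is an inference from the standard form of the method.

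On recording, the instruction to contact the principal investigator makes an unrecorded reaction less likely but does not rule it out.

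**Conclusion.** The point holds. The withdrawal rule is written out consistently in sections 9, 13 and 14, so it is not a slip, and nothing in the available text restores the lost data. The result is arm-specific loss after randomisation, possibly related to outcome and of unknown direction. The likely effect is small: at 1 of 50 withdrawn, at most 1.4 points in either direction across the two base risks. It reaches 6.7 to 7.9 points only in extreme 5-of-50 scenarios that the documents do not support. These sizes assume 50 per arm, no true effect and complete removal from the CINV analysis. The change should still be made, because it is cheap and outcomes not collected cannot be recovered later. The recording conflict is real for Grade 1 and 2 reactions and does not depend on any of these assumptions.

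**What to change.** 1. Leave the inhaler-stopping rule as it is. In sections 9, 13 and 14, replace withdrawal from the study with continued collection of the MAT, the diary and the final questionnaires at the infusion visits already scheduled, unless the participant withdraws consent.
2. State that a sensitivity answer given after randomisation is handled the same way in both arms for data collection and analysis.
3. In section 11, analyse everyone in the arm assigned using all available visits: a repeated-measures logistic model for the MAT outcomes and a mixed model for antiemetic use. The two-visit scales can be treated in the same way. A baseline alone says little about change, so collecting the final form matters most there.
4. For participants who decline further forms, add a sensitivity analysis counting their missing MAT results first all as events, then all as non-events.
5. Reconcile the two recording rules in section 14 for sensitivity reactions. Whichever is kept, report the number of sensitivity-related inhaler discontinuations by visit.

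The cost is a protocol amendment with ethics-board review, possibly revised consent wording, one analysis paragraph, and a few more forms from a handful of participants. The estimated effect may come out smaller, and some participants may decline to continue.

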- a) Primary Outcome
 - a) Outcome Measure Title: Reduction in severity of CINV
 - b) Outcome Measure Description: Assessed by the mean score of the Antiemesis (MAT) tool, which measures acute and delayed CINV across patients' chemotherapy regimens.
 - c) **Outcome Measure Timeframe**: Data tool collected during study visits 1, 2, 3, and 4.
- b) Secondary Outcome
 - a) Outcome Measure Title: Reduction in Antiemetic Use
 - b) **Outcome Measure Description**: Assessed by the mean score of antiemetics diary, which measures the usage frequency (date and time) and type (name) of antiemetic medications.
 - c) **Outcome Measure Timeframe**: Data diary collected during study visits 1, 2, 3, and 4.
- c) Exploratory Outcome
 - a) Outcome Measure Title: Improved Resilience
 - b) **Outcome Measure Description**: Assessed by the mean score of the Connor-Davidson Resilience Scale (CD-RISC), which measures the participants' resilience pre and post the intervention.
 - c) Outcome Measure Timeframe: Data collected at baseline and final visit.
- d) Exploratory Outcome
 - a) Outcome Measure Title: Reduction in Psychological Distress Symptoms
 - b) **Outcome Measure Description**: Assessed by the mean score of the psychological distress symptoms visual analog scale the patients' anxiety, stress, and depression at pre-and post-assessment.
 - c) Outcome Measure Timeframe: Data collected at baseline and final visit.
- e) Exploratory Outcome
 - a) Outcome Measure Title: Improved Quality of Life
 - b) **Outcome Measure Description**: Assessed by the mean score of Functional Assessment of Chronic Illness Therapy General (FACIT-G), which measures the

patients' quality of life and well-being at pre-and post-assessment.

c) Outcome Measure Timeframe: Data collected at baseline and final visit.

The study objectives and endpoints were selected because (a) more research is necessary to understand the effects of aromatherapy on moderate and high emetogenic chemotherapy regimens in an outpatient setting; (b) the literature suggests that CINV has a relationship with decreased quality of life and increased antiemetic usage and psychological distress symptoms; (c) the relationship between CINV and resilience has not been established. However, literature has shown a relationship between resilience and a reduction in psychological distress symptoms and improved quality of life.

9) Procedures Involved*

The study will continue as follows:

Initial visit

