A study team member and participant will meet during the participant's scheduled CTU appointment to collect their MAT tool and antiemetic/aromatherapy diary. During this interaction, the study team member will reinforce instructions and answer any participant's questions, concerns, or confusion regarding the aromatherapy inhaler, MAT tool, and antiemetic/aromatherapy diary. A new study packet and an aromatherapy inhaler, if necessary, will be provided to the participants.

Visit 3: Participants' visit three will take part on their next scheduled chemotherapy infusion – i.e., the participants' third chemotherapy cycle during their study period. A study team member

will give the participant access to complete the following assessments via iPad or laptop: postassessment and demographic form, psychological distress VAS, resilience scale, and FACIT-G.

Arm 1 - Control group:

A study team member and participant will meet during the participants' scheduled CTU appointment to collect their final MAT tool and antiemetic diary. During this interaction, the study team member will assess the participant's study experience and provide the participant with a thank you card appreciation for their study participation.

Arm 2 - Interventional group:

A study team member and participant will meet during the participants' scheduled CTU appointment to collect their final MAT tool and antiemetic/aromatherapy diary. During this interaction, the study team member will assess the participant's study experience and provide the participant with a thank you card appreciation for their study participation.

If a participant is admitted to an SCCC's inpatient unit or has their chemotherapy temporally held during their study period, the study procedures will be postponed until their next regularly scheduled outpatient CTU visit. Participants' known admissions will be noted in the respective participant's study notes.

Table 2

Timepoints	1	2	3	4
Visits	Initial	1	2	3 (Final)
Assessments collected on:				
Demographic	X*			
Pre-assessment	X*			
Psychological distress symptoms (VAS)	X*			X*
Resilience	X*			X*
FACIT-G	X*			X*
MAT tool		Х	Х	Х
Antiemetic diary		Х	Х	Х
Antiemetic/Aromatherapy diary (intervention group only)		Х	Х	Х
Post-assessment				X*

Participant's Study Period and Associated Assessments

Note: (*) indicates measures where data are entered directly in REDCap.

Interventions and Assessment Instruments:

Pre-Assessment and Demographic Checklist:

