Additionally, there is a space to name other complementary methods used to relieve CINV and describe how the CINV was controlled in the antiemetic/aromatherapy diary.

MAT Tool:

The Antiemesis (MAT) tool created by the Multinational Association of Supportive Care in Cancer (Dranisaris et al., 2017) is a user-friendly and reliable tool designed to measure acute and delayed CINV across patients entire chemotherapy regimen. The MAT tool is available in English and Spanish languages. The MAT tool consists of eight items that assess participants' CINV (i.e., occurrence, duration, and frequency). Four items assess the participants' acute phase (i.e., first 24 hours after receiving chemotherapy), and the last four items assess the delayed phase (i.e., day 2 to day 4 after chemotherapy treatment). The MAT tool has been used as a communication tool to facilitate discussions about their CINV to their healthcare providers (Alafafsheh & Ahmad, 2016; Molassiotis et al., 2007; Yamaguchi et al., 2009). This MAT tool has shown good reliability and validity, with Cronbach alpha of 0.77-0.97 in 1200 patients with cancer (Alafafsheh & Ahmad, 2016; Dranisaris et al., 2017; Molassiotis et al., 2007; Yamaguchi et al., 2009).

Antiemetic Diary (Arm 1 - Control Only):

The antiemetic diary allows the participants to record their usage (date and time) and type (name) of antiemetic medications. Additionally, there is a space to name other

complementary methods used to relieve CINV and describe how the CINV was controlled in the antiemetic diary.

Resilience Scale:

The Connor-Davidson Resilience Scale (CD-RISC) will assess the participants' resilience pre and post the intervention (Burns & Anstey, 2010). For this study, we will use the 10-item questionnaire that includes questions such as: are you 'able to adapt to change,' 'can (you) deal with whatever comes,' to 'can handle unpleasant feelings.' This scale has shown good reliability and validity, with Cronbach alpha of 0.88 in 343 patients with cancer and 122 breast patients with cancer (Matzka, Mayer, Köck-Hódi, Moses-Passini, Dubey, Jahn, ... & Eicher, 2016; Scali, Gandubert, Ritchie, Soulier, Ancelin, Chaudieu, & Uddin, 2012).

Psychological Distress Symptoms:

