A visual analog scale will be used to assess the patients' psychological distress symptoms of anxiety, stress, and depression at pre and post-assessment. Three individual visual analog scales of anxiety, stress, and depression will be measured on a 0 to 10 scale over the past 7-days (Benedetto, & Sheehan, 2014; Labaste et al., 2019; Lesage, Berjot, & Deschamps, 2012). The scale ranged from "0" (no anxiety, stress, and depression) to "10" (worst anxiety, stress, and depression). Visual analog scale is an accurate and sensitive tool to rate subjective symptoms. The visual analog scale has been found to be less burdensome for research participants. Studies have demonstrated that visual analog scale ratings were a reliable and validated instrument used to assess anxiety, stress, depression, and other symptoms, in a variety of patient populations (Benedetto, & Sheehan, 2014; Labaste et al., 2019; Lesage, Berjot, & Deschamps, 2012).

Quality of life:

Functional Assessment of Chronic Illness Therapy General (FACIT-G) measures patients' quality of life and well-being on a 27-item, four dimensions of health: physical, functional, social, and emotional well-being (Cella et al., 1993). The study will assess the patients' quality of life and well-being at pre and post-assessment timepoints. Questions range from 'I am forced to spend time in bed,' 'I feel close to my friends,' 'I worry about dying,' to 'I am able to enjoy life.' FACIT-G is a reliable and psychometric sound instrument with a Cronbach alpha of >0.89 that has been used in a variety of patients with cancer (Cella, 2012; Kin-Fong Cheng, 2006; Thomas, Pendey, Ramdas, Sebastian, & Nair, 2004).

Post-Assessment Questionnaire:

The participants will complete a post-assessment questionnaire on their final chemotherapy infusion. The post-assessment will evaluate the study and its instruments/tools. Questions range from 'Was the MAT tool easy to use,' 'Was the antiemetic diary easy to use,' to 'How likely are you to continue using aromatherapy.' The intervention group will be asked additional evaluation questions about the inhaler, the effects of the aromatherapy, and comments/suggestions.

10) Data and Specimen Banking*

This section is not applicable. This research is not banking data or specimens for future use.

11) Data Management*

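### Participants withdrawn from qualifying chemotherapy are labelled lost to follow-up, and the protocol gives no route to collect the MAT and diary for the last cycle they received

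*Combined protocol and SAP*

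**What the plan says.** Section 13 gives two routes to the label 'lost to follow-up'. One is a participant who cannot be reached: "if they stop communicating with the study team". The other is a treatment decision: "if the participant's oncologist withdraws them from IV moderate to high emetogenic chemotherapy".

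Section 9 (Procedures Involved, Initial visit) ties collection of the primary-outcome data to infusions: "The study packet will be completed and returned to the study team member on the participants' next scheduled chemotherapy infusion". Visits 1 to 3 repeat this. The distress VAS, CD-RISC and FACIT-G are repeated only at Visit 3, which is itself an infusion visit, described as "the participants' third chemotherapy cycle during their study period". These questionnaires are electronic: a study team member "will give the participant access to complete the following assessments via iPad or laptop".

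Under MAT Tool in the same section, the acute items cover the 24 hours after an infusion and the delayed items cover days 2 to 4.

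Sections 8 and 9 postpone study procedures if a participant is admitted or chemotherapy is temporarily held. Neither provides for permanent discontinuation.

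**The concern.** The label treats a change of therapy as loss of contact. If no further infusion follows, the occasion for handing in the last packet disappears, although the cycle it describes was given on the chemotherapy under study and the day 1 to day 4 period may be over.

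Eligibility requires nausea or vomiting after the first infusion (Section 5), so every participant already has the symptom being studied. Poor tolerance could be one reason for a change of treatment. If it is, the unreturned packets would tend to record worse CINV, and the gap would fall on the primary outcome and the antiemetic diary. At stake are precision and, under conditions set out below, the fairness of the arm comparison.

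**Working it through.** The plan states no figure on this point. Section 6 gives 100 participants with no power calculation or dropout allowance. The check is therefore a reading of the collection schedule, followed by illustrations on assumed rates.

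**1. What is in hand when treatment stops.** From Section 9 and Table 2, packets given out at the Initial visit, Visit 1 and Visit 2 are returned at Visits 1, 2 and 3.

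| Last infusion received at | Packets in hand under the stated route | With the last packet retrieved |
|---|---|---|
| Initial visit | 0 of 3 | 1 of 3 |
| Visit 1 | 1 of 3 | 2 of 3 |
| Visit 2 | 2 of 3 | 3 of 3 |

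In the first row the participant contributes no post-baseline MAT or diary, although one cycle was observable. In the last row retrieval completes the record.

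**2. Safeguards.** The postponement rule covers admission and temporary holds only. Section 11 (Data Management) has the team review missing data with the PI weekly, but gives no retrieval procedure, missing-data method or analysis set. The available text describes no early-termination visit and no telephone, postal or remote collection.

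**3. Effect on one arm's observed risk (all rates assumed).** Let d be the fraction whose packet is missing, S their CINV risk and O the risk among those observed. The true risk is T = (1 − d)O + dS.

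- d = 0.10, O = 0.60, S = 0.90: T = 0.9 × 0.60 + 0.1 × 0.90 = 0.63. The observed 0.60 is 3 points low. This needs all stopping to follow the same cycle.
- The same 10% spread evenly over three cycles gives d ≈ 0.033: T = 0.967 × 0.60 + 0.033 × 0.90 = 0.61, about 1 point per cycle.

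**4. Effect on the comparison.** Since T = O + d(S − O), the bias in the risk difference (aromatherapy, a, minus control, c) is d_c(S_c − O_c) − d_a(S_a − O_a). It is zero when the fraction missing and the stoppers' excess risk over those observed are the same in both arms.

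Illustration with T = 40% in both arms and S = 70%, using O = (T − dS)/(1 − d):

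- 20% missing in control, 10% in aromatherapy: (0.40 − 0.14)/0.80 = 32.5% against (0.40 − 0.07)/0.90 = 36.7%, a spurious 4.2 points.
- 30% against 10%: (0.40 − 0.21)/0.70 = 27.1% against 36.7%, or 9.5 points.
- 20% in both: 32.5% in each, a difference of 0.

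These also put all stopping in one cycle. Spreading the first case over three cycles (6.7% against 3.3%) gives (0.40 − 0.067 × 0.70)/0.933 = 37.9% against (0.40 − 0.033 × 0.70)/0.967 = 39.0%, about 1.1 points per cycle. The sign reverses if the imbalance does.

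**5. Precision (assuming 1:1 allocation and two-sided 0.05).** The standardised difference detectable with 80% power is (1.96 + 0.84) × √(2/n), with n per arm.

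| Loss per arm | n per arm | Detectable difference | Power for 0.56 |
|---|---|---|---|
| 0% | 50 | 0.56 | 80% |
| 10% | 45 | 0.59 | 76% |
| 20% | 40 | 0.63 | 71% |
| 30% | 35 | 0.67 | 65% |

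This is the cost when whole participants leave an analysis. Losing one cycle's packet costs less.

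**The case against.** The strongest reply is that Section 13 only assigns a label. It does not say that collection stops, that outstanding packets are discarded or that the participant leaves the analysis. The weekly review leaves room to chase a packet, and the return point in Section 9 is not limited to moderate-to-high emetogenic regimens, so someone switched to a milder infusion still has one. All this stands against a reader who infers that the data are never collected. It does not supply a route: nothing tells staff to pursue a participant already classed as lost, and those with no further infusion have no return point.

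Second, a reader might count the final VAS, CD-RISC and FACIT-G as recoverable outcomes simply lost. The hypotheses in Section 3 concern patients while they receive qualifying chemotherapy. Answers given after stopping describe a different state and cannot stand in for Visit 3 unless the plan says how they are used. This objection stands.

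Third, a reader might infer that the analysis drops the whole participant. Section 11 analyses CINV by logistic regression and does not say how a missing cycle is handled. The Mixed ANOVA applies to antiemetic use and the questionnaire scales. Complete-case handling is its conventional form but is not stated. Even if it is used, retrieving the last packet completes the diary record only for those who stop after the Visit 2 infusion; earlier stoppers still lack later cycles.

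Fourth, no stopping rate, reason for stopping or arm imbalance appears in the documents. That also stands.

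**Conclusion.** The concern holds as a gap in data collection. Reachable participants share a label with unreachable ones, and the protocol provides no route to the MAT and diary for the last cycle they received, even where the reporting window has closed. The missingness may be related to CINV or tolerability; the documents do not show that it is.

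The size is undetermined. Under the assumed rates, the within-arm shift is about 1 point per cycle when stopping is spread over the study and 3 points when it is concentrated after one cycle. A reader might infer that the treatment comparison is biased. The documents do not support that: it requires stopping, or stoppers' outcomes relative to those observed, to differ by arm. Without such a difference the loss is one of precision. The bias figures are on the risk-difference scale, whereas the planned logistic regression works on odds.

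The change is worth making because it is cheap and because packets not retrieved promptly may not be recoverable at analysis.

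**What to change.** - In Section 13, keep 'lost to follow-up' for participants who cannot be reached, and add a separate category, 'qualifying chemotherapy discontinued', with date and reason.
- In Section 9, state that when this occurs the team retrieves the outstanding MAT and diary packet at that point by telephone, post or REDCap link.
- In Section 11, state that these participants stay in the analysis as randomised with all cycles received, and that discontinuations and reasons are reported by arm.
- Optionally, collect the final VAS, CD-RISC and FACIT-G remotely at the same contact, flagged as completed off qualifying chemotherapy, with their use stated in advance (for example, a sensitivity analysis).

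The change concerns data collection only and leaves treatment decisions untouched. It costs protocol wording and one remote contact per affected participant: 5 to 15 contacts among 100 if 5% to 15% stop (assumed). Table 2 marks the final questionnaires as entered directly in REDCap, but not the MAT or diaries, so a REDCap link for the packet would need a form to be built; telephone or post would not.
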